## 6.3 Conventions

All data listings, summaries, figures and statistical analyses will be generated using SAS version 9.4 or higher.

Summaries will be presented by treatment group and/or overall. Treatment group labels will be displayed as follows for Part 1:

SENS 29mg                      SENS 43.5mg                      Placebo

For Part 2, treatment group labels will be displayed as follows:

SENS XXmg                      Placebo

	Sponsor:	Sensorion
	Protocol Number:	SENS 401-201
STATISTICAL ANALYSIS PLAN. PHASE 2-3-4		

Overall columns are to be included within the table shells as follows:

Data	Columns labels
Demography	Treatment groups and overall
Baseline	Treatment groups and overall
Disposition	Treatment groups and overall
Efficacy	Treatment groups
Pharmacokinetic (PK)	Treatment groups
PD	Treatment groups
AEs	Treatment groups and overall
Other safety	Treatment groups

Listings will be sorted in the following order: treatment group, subject, parameter, and visit, unless otherwise stated. All data will be listed, subjects who were not randomized will be displayed after the randomized treatment groups.

Continuous variables will be summarized by the number of non-missing observations, mean, median, standard deviation, and minimum and maximum. For all tabulations of changes from baseline data, the lower and upper 95% confidence limits for the mean for the individual treatments will be given.

Categorical variables will be summarized by presenting the frequency and percent. Percentages will be based on the number of non-missing observations or the subject population unless otherwise specified. For each variable, all categories will be shown. Zero frequencies (but not the percent) within a category will be presented.

### 6.3.1 Decimal Places

Decimal places for derived data described in Section 6.2 will be determined by the scale of measurement unless otherwise stated. No decimal places will be displayed if the smallest calculated value is  $\geq 100$ ; 1 decimal place will be displayed when the smallest value is within the interval (10, 100), with 10 being inclusive; 2 decimal places will be displayed when the smallest value is within (1, 10), with 1 being inclusive; and so on for even smaller scales of measurement.

Derived data where it is known in advance the result will be an integer for example day, month, year, number of days and total scores (for rating scales) will be presented with zero decimal places.

	Sponsor:	Sensorion
	Protocol Number:	SENS 401-201
STATISTICAL ANALYSIS PLAN. PHASE 2-3-4		

Means, medians and percentiles will be displayed to one more decimal place than the data, dispersion statistics (e.g. standard deviation) will have two more decimal places, and the minimum and maximum will be displayed to the same number of decimal places as reported in the raw data. Percentages will be displayed with one decimal place.

P- Values will be quoted to 4 decimal places. P-values < 0.0001 will be presented as p<0.0001.

#### **6.4 Subject Disposition**

For each part of the study, subject disposition will be summarized by center and overall (i.e. across centers) as follows:

- The number of subjects who failed screening and the reasons for failure will be tabulated for all screened subjects.
- The number of subjects randomized, and number of subjects in each analysis set will be summarized by treatment group and overall based on the ITT set.
- The number of early withdrawals and the reason for withdrawals will be tabulated by treatment group and overall based on the ITT set.

#### **6.5 Protocol Deviations**

Protocol deviations will be classified as Major, Minor, or Critical. Additionally, any COVID-19-related protocol deviations will be identified. A tabulation of the number of protocol deviations within each classification will be presented by treatment group and overall for the ITT analysis set. A listing of protocol deviations will be provided within Appendix 16.2 of the CSR.

#### **6.6 Stratification factors**

For each part of the study, the distribution of the subjects across the categories of each of the 3 stratification factors (site category (non-ancillary, ancillary), duration of disease (< 24 hours, ≥24 hours), and oral corticosteroids intake at baseline (yes, no)), will be summarized by randomized treatment group and overall based on the ITT analysis set.

#### **6.7 Baseline Comparability**

The comparability of treatment groups with respect to subject demographics and baseline characteristics will be assessed in a descriptive manner, but no formal statistical testing will be performed.

	Sponsor:	Sensorion
	Protocol Number:	SENS 401-201
STATISTICAL ANALYSIS PLAN. PHASE 2-3-4		

For each part of the study, standard continuous or categorical variable summaries will be presented by randomized treatment group and overall based on the ITT analysis set.

All baseline data will also be listed.

### 6.7.1 Demographics

The following variables will be summarized:

- age at informed consent (years)
- gender
- fertility status (female subjects)
- ethnicity
- race
- height (cm)
- weight (kg)
- BMI (kg/m^2)

### 6.7.2 Disease Characteristics and Other Relevant Baseline Data

The following variables will be summarized:

- Duration of current hearing loss episode at time of randomisation (in hours): randomisation date/time-SSNHL onset date/time, continuous and by class (<24 hours, [24; 48[, [48; 72[, >72 hours)
- Cause of current hearing loss/SSNHL: idiopathic, trauma (including noise induced), infectious, otologic disease, ototoxic drug intake, vascular/hematologic, neoplastic
- Oral Corticosteroids (CM.CMCAT = “ORAL STEROID”) for SSNHL (CM.CMINDC = “SSNHL”) at baseline (ongoing or started the day of first study treatment intake): yes/no and type (prednisone/prednisolone, methylprednisolone, dexamethasone or other)
- Otologic history: ear used for telephone and recent switch, professional exposure to very loud noise, recreational exposure to very loud noise, history of severe ear problems (previous SSNHL, frequent otitis media, past history of ear surgery, wearing hearing aids, past history of tinnitus in each ear), ear/head/neck/nose/throat problems (infection, respiratory tract infection, ear pain, ear pressure, otorhea, severe headache or migraine, recent head or neck trauma, recent baro trauma, exposure to loud noise, past otologic evaluation)

	Sponsor:	Sensorion
	Protocol Number:	SENS 401-201
STATISTICAL ANALYSIS PLAN. PHASE 2-3-4		

- Baseline Pure Tone Audiometry air conduction average of the hearing threshold of 3 contiguous most affected hearing frequencies in decibels as identified at study entry (PTA) for the current hearing loss episode:
  - Initial frequency range ( $\leq 2000$  Hz,  $> 2000$  Hz) derived as the mean between the lowest and the highest of the most affected frequencies
  - Affected ear side (right, left)
  - Affected ear PTA continuous (in decibels)
  - Affected ear PTA by class ( $<20$  dB,  $\geq 20$  dB to  $\leq 35$  dB,  $>35$  dB to  $\leq 50$ dB,  $>50$  to  $\leq 70$  dB,  $>70$  to  $\leq 90$  dB,  $>90$  dB)
  - Reference type (contralateral ear, previous PTA, reference frequency)
  - Reference PTA continuous
  - Reference PTA by class
  - Hearing loss (difference between the PTA on affected ear and the reference PTA for the identified frequencies) continuous (in decibels)
  - Hearing loss by class according to American Speech-Language-Hearing Association criteria (ASHA) ( $<16$ , 16 to  $<26$ dB, 26 to  $<41$ dB, 41 to  $<56$ dB, 56 to  $<71$ dB, 71 to  $<91$ dB,  $\geq 91$ dB)
- Tinnitus numeric rating scale (NRS) as recorded in the eCRF (XT.XTCAT=“Questionnaire”): score (from 0 to 10)
- Vertigo NRS: score (from 0 to 10)
- Speech recognition threshold (SRT) on affected ear: minimum hearing level at which the patient can correctly recognizes 50 % of the presented speech material
- Word recognition score (WRS) also called Speech discrimination score on affected ear: percentage of words correctly repeated at 60dB and 80dB
- Tinnitus functional index (TFI) Total Score (from 0 to 250)

## 6.8 Medical/Surgical History

For each part of the study, separate tabulations of previous and ongoing medical and surgical conditions at screening will be presented by randomized treatment group and overall, for the ITT analysis set. Conditions will be presented by Medical Dictionary for Regulatory Activities (MedDRA) primary system organ class and preferred term, using the most recent MedDRA version available at the time of database lock.

All data will be listed.

	Sponsor:	Sensorion
	Protocol Number:	SENS 401-201
STATISTICAL ANALYSIS PLAN. PHASE 2-3-4		

## 6.9 Prior and Concomitant Medications

For each part of the study, separate tabulations will be produced for prior and concomitant medications presented by randomized treatment group and overall, for the Safety analysis set. Prior medications are defined as all medications that started and stopped before the date of first dose of study drug. Concomitant medications are defined as medications that started prior to, on or after the date of first dose of study drug and ended on or after the date of first dose of study drug or are ongoing at end of study. Prior and concomitant medications will be summarized using Anatomic Therapeutic Chemical (ATC) Level 2. All medications will be coded using the most recent version of the WHO Drug Dictionary available at the time of database lock.

A separate tabulation for study treatment concomitant medications, defined as medications that started before date of the first dose of study drug and continued while on study drug or medications that started between the day of the first dose of study drug (included) and the date of the last dose of study drug (included) will be displayed by randomized treatment group and overall, for the Safety analysis set.

A separate tabulation for prior and concomitant use of oral corticosteroids (excluding use as rescue medication) will be displayed by randomized treatment group and overall, for the Safety analysis set.

A separate tabulation for concomitant corticosteroid as rescue treatment will be tabulated. Supporting dosing information will be listed, along with the other prior and concomitant medications.

## 6.10 Exposure to Study Drug

Extent of exposure (number of days of exposure to study drug) will be presented by randomized treatment group for the Safety analysis set.

## 6.11 Treatment Compliance

Overall percent compliance to study drug dosage regimen, calculated as percent doses taken relative to doses scheduled to be taken, that is,

$$\frac{(\text{Total Dispensed} - \text{Total Returned}) \times 100}{3 * 2 * \text{Extent of exposure to study drug}}$$

	Sponsor:	Sensorion
	Protocol Number:	SENS 401-201
STATISTICAL ANALYSIS PLAN. PHASE 2-3-4		

where the “Total Dispensed” is 180 and “Total Returned” is the sum of the Blue label, Yellow label, and Green label tablets returned by patient. Subject compliance will be summarized by treatment group for the Safety analysis set.

## 6.12 Efficacy Analyses

For Part 1 all statistical tests will be performed using a one-tailed 5% significance level. All comparisons between treatments, where high dose vs. placebo will be tested first, and then testing conditionally low dose vs. placebo, will be reported with 90% confidence intervals for the difference.

For Part 2, all statistical tests will be performed using a two-tailed 5% significance level. All comparisons between treatments will be reported with 95% confidence intervals for the difference.

### 6.12.1 Primary Endpoint

The primary endpoint is the change in pure tone audiometry (PTA: average of the hearing threshold of 3 contiguous most affected hearing frequencies in decibels as identified at study entry) on pure tone audiometric air conduction testing in the affected ear from baseline to the end of treatment visit (Visit D28 ± 3).

The 3 most affected contiguous audiometric test frequencies are defined with respect to the unaffected contralateral ear and will be fixed for all further calculations. In case of a pre-existing contralateral hearing loss, the corresponding values of a pre-existing audiogram of the affected ear, if dating back less than 2 years, will be considered as the reference. For all other scenarios (e.g. pre-existing contralateral hearing loss with no audiogram in the past 2 years) the reference frequencies will be set using the ISO 7029;2017 norm values. In case of bilateral acute acoustic trauma leading to sudden sensorineural hearing loss, the most affected ear according to the inclusion criteria will be considered. If both ears are equally affected, the right ear will be considered.

At baseline, if 2 or more sequences of 3 contiguous frequencies are similarly affected, the index sequence with the lower contiguous frequencies will be selected as the reference. Pure tone average frequencies determined at baseline will remain fixed for all evaluations.

If one of the frequencies is missing for post baseline values the PTA will be averaged on 2 out of the 3 identified frequencies. If more than 1 is missing, the PTA will not be calculated.

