### 8.1 Inclusion criteria

1. Male or female
2. Aged at least 18 years old
3. Patients with unilateral idiopathic sudden sensorineural hearing loss or unilateral/bilateral acute acoustic trauma leading to SSNHL defined by both:
  - 3.1. At least 1 hearing threshold of 50 dB or more among the 3 most affected contiguous frequencies on pure tone audiometric air conduction testing performed 24 hours or less prior to first study treatment), and
  - 3.2. Mean hearing loss of 30 dB or more, averaged across the 3 most affected contiguous frequencies on pure tone audiometric air conduction testing (PTA: Pure Tone Average) performed 24 hours or less prior to first study treatment), compared with the unaffected contralateral ear or reference values from a pre-existing audiogram (dated less than 2 years)
4. Patients with sudden hearing loss with onset within 96 hours prior to prior to first study drug intake.
5. Females must meet 1 of the following: Postmenopausal defined as 12 consecutive months with no menses without an alternative medical cause or Surgically sterile or Abstinent or Practicing **highly** effective birth control (must agree to use 2 forms of contraception [1 of which must be a barrier method]) (Appendix 4) and willing to continue to use **highly** effective contraception for the duration of study participation and for 30 days after the final dose of study drug). Women of childbearing potential must have a negative pregnancy test at screening before the first dose of study drug is taken. Women of childbearing potential are defined as any female who has experienced menarche and who is not permanently sterile or postmenopausal.
6. Male subjects and their female partner(s) must agree to use highly effective contraception (must agree to use 2 forms of contraception [1 of which must be a barrier method]) (Appendix 4) for the duration of study participation and for 90 days after the final dose of study drug.
7. Signed and dated written informed consent.

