**The hearing threshold** is defined as the lowest audible level, measured twice out of three presentations for that patient. The thresholds at each frequency for each ear for both air and bone pure tone audiometry will be recorded on the e-CRF at each study visit. The information will be captured in case of no response because of profound hearing loss.

The **hearing loss** will be determined as follows: Difference between the mean hearing threshold at the 3 most affected contiguous test frequencies (air pure tone average) and the corresponding mean hearing threshold of the contralateral ear or values from a pre-existing audiogram (dated less than 2 years) for the same frequencies (mandatory for bilateral acute acoustic trauma).

The Pure tone average frequencies determined at baseline will remain fixed for all evaluations. In case of bilateral acute acoustic trauma leading to sudden sensorineural hearing loss, the most affected ear according to the inclusion criteria will be considered for the analysis. If both ears are equally affected, the right ear will be considered.

In case of one missing frequency in any of the post baseline measurement, the PTA will be determined on the 2 out of the 3 available frequencies. An absolute improvement of 10dB is considered clinically meaningful.

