### 13.4 Handling of missing data:

The primary end-point is the absolute change in PTA (in dB) from baseline to the end of treatment visit (D28) based on the average on the 3 most affected contiguous audiometric test frequencies identified at baseline.

The 3 most affected contiguous audiometric test frequencies are the reference and will remain fixed for all further calculations. They are defined according to the unaffected contralateral ear or values of a pre-existing audiogram dated less than 2 years.

At baseline, if 2 or more sequences of 3 contiguous frequencies are similarly affected, the index sequence with the lower contiguous frequencies will be selected as the reference.

If one of the frequency is missing for post baseline values, the PTA will be determined on 2 out of the 3 identified frequencies. If more than 1 is missing, the PTA will not be calculated.

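### Read literally, SAP 6.12.1 sends bilateral acute acoustic trauma to ISO 7029 norms even when the audiogram the protocol makes mandatory is on file; the change is undeclared, and its effect is probably small

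*SAP*

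**What the plan says.** Bilateral acute acoustic trauma is eligible. Inclusion criterion 3 (protocol 8.1) admits "unilateral/bilateral acute acoustic trauma leading to SSNHL defined by both" audiometric conditions, and only bilateral idiopathic loss is excluded (protocol 8.2).

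Protocol 10.1.1 measures hearing loss against the contralateral ear or "values from a pre-existing audiogram (dated less than 2 years) for the same frequencies (mandatory for bilateral acute acoustic trauma"). Protocol 13.4 says of the three index frequencies: "They are defined according to the unaffected contralateral ear or values of a pre-existing audiogram dated less than 2 years". It offers no normative reference.

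SAP 6.12.1 has three steps:

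1. "The 3 most affected contiguous audiometric test frequencies are defined with respect to the unaffected contralateral ear".
2. "In case of a pre-existing contralateral hearing loss, the corresponding values of a pre-existing audiogram of the affected ear" are the reference, if less than 2 years old.
3. "For all other scenarios (e.g. pre-existing contralateral hearing loss with no audiogram in the past 2 years"). For every such case the SAP falls back on population norms: "the reference frequencies will be set using the ISO 7029;2017 norm values".

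The SAP's sentence on bilateral trauma says only which ear is analysed. The index frequencies then stay fixed at every visit. SAP section 8, which lists departures from the protocol down to a change from plural to singular, does not mention ISO norms.

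**The concern.** The SAP's residual rule overrides the protocol for an eligible subgroup, in the definition of the primary endpoint. The endpoint is the change in the affected ear's own thresholds, so the reference matters only through which three frequencies it selects. That choice is permanent. The patient's own recent audiogram removes old loss from the selection; a population norm does not. Old high-frequency loss can then count as part of the acute episode, and the endpoint can be placed where little recovery is possible. Protocol 5.2 itself describes loss of auditory hair cells as irreversible. Exclusion criterion 3 screens for known asymmetry above 20 dB, so it does not catch an earlier loss that is symmetric.

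The reference has two further uses. It sets the baseline hearing-loss summary (SAP 6.7.2), and it sets the rule for hearing similar to the unaffected ear in the recovery endpoint (SAP 6.12.5.1), which the SAP applies to normative references as well.

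**Working it through.** **1. Applying the SAP rule to a bilateral acute trauma patient with a valid audiogram**

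| SAP step | Condition | Met? |
|---|---|---|
| Contralateral ear | it is unaffected | No, both ears are affected |
| Own audiogram, under 2 years | contralateral loss is pre-existing | No, the contralateral loss is acute |
| ISO 7029 | any other scenario | Yes |

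Under protocol 10.1.1 and 13.4 the same patient is referred to the audiogram. The two documents give different references.

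**2. Can the reference move the window?** All thresholds and norms here are assumed; the documents print no ISO values. For each run of three contiguous frequencies among 0.25, 0.5, 1, 2, 3, 4, 6 and 8 kHz, take the mean of (current minus reference) and choose the largest, with ties going to the lower frequencies as the SAP says. Recoverable loss is the mean of (current minus own audiogram) in the chosen window.

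*Patient A.* Audiogram 5/5/5/10/40/50/50/45 dB; now 50/50/50/50/60/65/65/60 dB.
- Own audiogram: differences 45/45/45/40/20/15/15/15. The window is 0.25-0.5-1 kHz, with 45 dB recoverable.
- Flat norm of 0 dB: 3-4-6 kHz scores (60+65+65)/3 = 63.3 dB and ties with 4-6-8 kHz; 0.25-0.5-1 kHz scores 50.0 dB. The window is 3-4-6 kHz, with (20+15+15)/3 = 16.7 dB recoverable.
- Steeper norm of 0/0/0/5/10/15/20/25 dB: 0.25-0.5-1 kHz scores 50.0 dB and 3-4-6 kHz scores (50+50+45)/3 = 48.3 dB. The window is the same as with the audiogram, and nothing is lost.
- Between these two windows the switch point is 63.3 - 50.0 = 13.3 dB. The window moves to 3-4-6 kHz only if the norm averages less than 13.3 dB higher there than at 0.25-1 kHz.

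*Patient B.* Audiogram 10/10/10/10/25/60/65/60 dB; now 10/15/45/60/65/75/75/70 dB.
- Own audiogram: 1-2-3 kHz, with (35+50+40)/3 = 41.7 dB recoverable.
- Norm of 5/5/5/5/10/10/15/15 dB: 3-4-6 kHz scores (55+65+60)/3 = 60.0 dB, with (40+15+10)/3 = 21.7 dB recoverable.
- Steeper norm as above: 2-3-4 and 3-4-6 kHz tie at 170/3 = 56.7 dB, so 2-3-4 kHz is chosen, with (50+40+15)/3 = 35.0 dB recoverable.

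The window can move, but whether it does, and at what cost, depends on the audiogram's shape and the norm's slope.

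**3. Effect on power.** Inputs from SAP sections 4 and 7: difference 15 dB, SD 26.79 dB (30 × √(1 - 0.45²)), one-sided 5%, power 75%.

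Plan's figure: n per arm = 2(1.645 + 0.674)² × (26.79/15)² = 34.3, rounded up to 35, or 105 in total. This reproduces the stated fixed design.

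Power at 35 per arm: standard error 26.79 × √(2/35) = 6.404; 15/6.404 - 1.645 = 0.697; power 75.7%.

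If a share q of patients loses half the effect, the mean difference is 15 × (1 - q/2):

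| q (assumed) | Difference, dB | Power |
|---|---|---|
| 0 | 15.00 | 75.7% |
| 2% | 14.85 | 75.0% |
| 5% | 14.63 | 73.9% |
| 10% | 14.25 | 71.9% |

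For Part 2 (10 dB, SD 20, two-sided 5%, 85 evaluable per arm, and 85/0.9 rounded up to 95 as stated), the same 2% and 5% take power from 90.3% to 89.7% and 88.8%.

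**4. Plausible share.** The documents do not give the bilateral share. Protocol 5.1 puts trauma of all kinds at 4.2% of SSNHL and idiopathic cases at 71%. Within those two groups trauma is 4.2/75.2 = 5.6%, or about 6 of 111 patients if enrolment mirrors those figures. Bilateral acoustic trauma is a subset of that, and those with a window-shifting earlier loss are a smaller subset again.

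**The case against.** The SAP never says that bilateral trauma uses ISO norms; that follows only from its residual wording. The one example it gives there is a patient without a recent audiogram, which suggests that the norms were meant for missing audiograms. The ear is chosen by the inclusion criteria, and criterion 3.2 knows only the contralateral ear or an audiogram. The endpoint uses frequencies identified at study entry, and SAP 6.2 says that variables derived in the source data are not recalculated unless otherwise stated. Reference type, ISO included, is tabulated by treatment group (SAP 6.12.2), so any use of norms would be visible.

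This shows that the intent is ambiguous. It does not displace the text: the inclusion-criteria phrase governs the choice of ear, an example does not limit a clause covering all other scenarios, and a programmer will follow the words. Tabulation reveals the problem only after the windows are fixed.

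A reader might go further and infer that the sponsor deliberately replaced the audiogram with norms, that every bilateral patient is harmed, or that the best achievable change typically falls from 45 to about 17 dB. The documents support none of these. Intent is not stated. Harm needs an earlier loss of a particular shape. The 45 to 17 dB contrast vanishes under an assumed steeper norm.

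**Conclusion.** The contradiction stands on the text. For bilateral acute acoustic trauma, SAP 6.12.1 as worded applies a reference that protocol 10.1.1 and 13.4 do not allow, and SAP section 8 does not declare it. Because the rule fixes the frequencies of the primary endpoint, it should be corrected, even if it is only a drafting gap.

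The size is unknown and probably small. It depends on three things the documents do not give: the share of bilateral trauma, how many of those patients have an earlier loss that shifts the window, and the norm values. The power figures also assume that each affected patient loses half the effect. The same rule applies at baseline in every arm, so the consequence is non-differential dilution. A reader should not infer a bias for or against SENS-401, or a material loss of power; at the assumed 2% to 5%, Part 1 loses about 1 to 2 percentage points.

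**What to change.** - In SAP 6.12.1, extend the audiogram step to cover bilateral acute acoustic trauma as well as pre-existing contralateral hearing loss, using the affected ear's own audiogram if under 2 years old.
- Restrict ISO 7029 to patients with neither a usable contralateral ear nor such an audiogram.
- List the ISO fallback in SAP section 8 as a departure from the protocol.
- Bring the separate GST and DMC SAPs into line, so that the same patient has the same index frequencies in every analysis. The first GST look has already been done; record which rule it used.
- Optionally, repeat the primary analysis without ISO-referenced patients.

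The cost is a clause of SAP text, one derivation to amend before unblinding, and a consistency check across the three plans. No new data are needed, because the protocol already requires the audiogram for these patients and reference type is already tabulated.
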